3.4 DISCONTINUATION OF SUBJECTS FROM TREATMENT OR ASSESSMENTS

Subjects may discontinue trial treatment or withdraw consent to trial participation as a whole (“withdrawal of consent”) with very different implications; please see sections [3.4.1](#) and sections [3.4.2](#) below. However, if the subjects agree, they should stay in the trial. Even if continued trial treatment is not possible, they should attend further trial visits to ensure their safety and to collect important trial data.

Measures to control the withdrawal rate include careful patient selection, appropriate explanation of the trial requirements and procedures prior to trial enrolment, as well as the explanation of the consequences of withdrawal.

The decision to discontinue trial treatment or withdraw consent to trial participation and the reason must be documented in the patient files and CRF. If applicable, consider the requirements for AE collection reporting (please see section [5.2.6.2](#)).

3.4.1 Discontinuation of trial treatment

An individual subject will discontinue trial treatment if any of the following criteria apply:

Healthy subjects and F4 liver cirrhosis patients

1. The subject wants to discontinue trial treatment, without the need to justify the decision
2. The subject has repeatedly shown to be non-compliant with important trial procedures and, in the opinion of both, the investigator and sponsor representative, is not willing or able to adhere to the trial requirements in the future
3. The subject needs to take concomitant medication (except from already discussed baseline medication for standard of care per local guidelines)
4. In addition to these criteria, the investigator may discontinue subjects at any time based on his or her clinical judgment
5. The participant experiences an infection with SARS-CoV-2 as confirmed by the COVID-19 rapid test at the admission to the trial site or based on the investigator's judgement on day 1.

3.4.2 Withdrawal of consent to trial participation

Subjects may withdraw their consent to trial participation at any time without the need to justify the decision.

If a subject wants to withdraw consent, the investigator should be involved in the discussion with the subject and explain the difference between trial treatment discontinuation and withdrawal of consent to trial participation, as well as explain the options for continued follow-up after trial treatment discontinuation.

3.4.3 Discontinuation of the trial by the sponsor

Boehringer Ingelheim reserves the right to discontinue the trial overall or at a particular trial site at any time for the following reasons:

1. Failure to meet expected enrolment goals overall or at a particular trial site
2. Violation of GCP, or the CTP, or the contract with BI impairing the appropriate conduct of the trial
3. The sponsor decides to discontinue the trial due to business reasons

The investigator/trial site will be reimbursed for reasonable expenses incurred in case of trial termination (except in case of the third reason).

4. TREATMENTS

4.1 INVESTIGATIONAL TREATMENTS

Rosuvastatin, digoxin, metformin and furosemide will be obtained from a public pharmacy.

Trial product 1

Name: *CRESTOR® 10 mg Film-coated tablet
Substance: Rosuvastatin (as rosuvastatin calcium)
Pharmaceutical formulation: Film-coated tablet
Holder of marketing authorization: AstraZeneca GmbH, Germany
Unit strength: 10 mg
Posology: 1 – 0 – 0 (cocktail component)
Route of administration: Oral
Duration of use: single dose on Day 1

Trial product 2

Name: *Lanicor® 0,25 mg tablets
Substance: Digoxin
Pharmaceutical formulation: Tablet
Holder or marketing authorization: Teofarma S.r.l., Italy
Unit strength: 0.25 mg
Posology: 1 – 0 – 0 (cocktail component)
Route of administration: Oral
Duration of use: single dose on Day 1

Trial product 3

Name: *MetfoLiquid GeriaSan® 1000 mg/5 ml oral solution
Substance: Metformin hydrochloride
Pharmaceutical formulation: Oral solution
Holder of marketing authorization: Rosemont Pharmaceuticals Ltd, United Kingdom
Co-marketing: INFECTOPHARM Arzneimittel und Consilium GmbH, Germany
Unit strength: 1000 mg/5 mL
Posology: 0.05 mL (10 mg) – 0 – 0 (cocktail component)
Route of administration: Oral
Duration of use: single dose on Day 1

Trial product 4

Name: *Lasix® liquidum 10 mg/ml oral solution
Substance: Furosemide (as furosemide sodium)
Pharmaceutical formulation: Oral solution
Holder of marketing authorization: Sanofi-Aventis Deutschland GmbH, Germany
Unit strength: 10 mg/mL
Posology: 0.1 mL (1 mg) – 0 – 0 (cocktail component)
Route of administration: Oral
Duration of use: single dose on Day 1

* These trial products may be replaced by generics which will be announced via a non-substantial CTP amendment.

4.2 SELECTION OF DOSES IN THE TRIAL AND DOSE MODIFICATIONS

Based on results of trials 0352-2082 [[c02586759-02](#)], 0352-2094 [[c08983809-01](#)], 0352-2096 [[c13060859-01](#)], and 0352-2100 [[c23988236-01](#)] the established cocktail of drug transporter substrates consists of 0.25 mg digoxin, 1 mg furosemide, 10 mg metformin hydrochloride and 10 mg rosuvastatin (see section [1.2](#)).

4.3 METHOD OF ASSIGNING PATIENTS TO TREATMENT GROUPS

After the assessment of all in- and exclusion criteria, each eligible subject will receive a single dose of the cocktail. Everyone will receive the same doses.

4.3.1 Drug assignment and administration of doses for each patient

This trial is an open label, non-randomised, single dose study. All subjects will receive a single dose of the cocktail. The treatments to be evaluated are outlined in [Table 4.3.1: 1](#) below.

Table 4.3.1: 1 Dosage and treatment schedule

Treatment	Substance	Formulation	Unit strength	Dosage	Total daily dose
Cocktail	Digoxin	Tablet	0.25 mg	1 tablet as single dose	0.25 mg
	Furosemide	Oral solution	10 mg/mL	0.1 mL (1 mg) as single dose	1 mg
	Metformin	Oral solution	1000 mg/5 mL	0.05 mL (10 mg) as single dose	10 mg
	Rosuvastatin	Film-coated tablet	10 mg	1 tablet as single dose	10 mg

Standardized light breakfast

A standardized meal (bread roll or similar with butter, cheese and/or sliced sausage) will be served 1 h 30 min before the cocktail is administered.

[REDACTED]

After cocktail administration

Subjects will be kept under close medical surveillance until [REDACTED] following cocktail administration.

[REDACTED]

4.3.2 Blinding and procedures for unblinding

This Phase I trial will be handled in an open fashion throughout (that is, during the conduct, including data cleaning and preparation of the analysis). This is considered acceptable because the potential for bias seems to be low and does not outweigh practical considerations. Emergency envelopes will not be provided, because the dose of trial medication is known to investigators and subjects.

4.3.3 Packaging, labelling, and re-supply

Rosuvastatin, digoxin, metformin and furosemide will be obtained by the clinical trial site from a public pharmacy. The drug will be dispensed out of the original, unmodified packages.

4.3.4 Storage conditions

Drug supplies will be kept in their original packaging and in a secure limited access storage area in accordance with the recommended (labelled) storage conditions. If necessary, a temperature log must be maintained to make certain that the drug supplies are stored at the correct temperature. If the storage conditions are found to be outside the specified range, the local clinical monitor (as provided in the list of contacts) is to be contacted immediately.

4.3.5 Drug accountability

Only authorised personnel documented in the trial team log may dispense medication to trial subjects. The trial medication must be administered in the manner specified in the CTP. The investigator or designee must maintain records of the product's delivery to the trial site, the inventory at the site, the use by each subject, and the disposal of unused products. These records will include dates, quantities, batch/serial numbers, expiry ('use-by') dates, and the

unique code numbers assigned to the investigational medicinal product and trial subjects. The investigator or designee will maintain records that document adequately that the subjects were provided the doses specified by the CTP and reconcile all investigational medicinal products. At the time of disposal of remaining trial medication, the investigator or designee must verify that all unused or partially used drug supplies have been disposed of.

4.4 OTHER TREATMENTS, EMERGENCY PROCEDURES, RESTRICTIONS

4.4.1 Other treatments and emergency procedures

There are no special emergency procedures to be followed. No additional treatment is planned. However, if AEs require treatment, the investigator can authorise symptomatic therapy. In those cases, subjects will be treated as necessary and, if required, kept under supervision at the trial site or transferred to a hospital until all results of medical evaluations are acceptable.

4.4.2 Restrictions

4.4.2.1 Restrictions regarding concomitant treatment

[REDACTED]

[REDACTED]

[REDACTED]

4.4.2.2 Restrictions on diet and lifestyle

A high-contrast, black and white image showing a series of horizontal white bars of varying lengths against a black background. The bars are positioned in a staggered, non-linear pattern, creating a sense of depth or a stylized data visualization. The bars are thick and appear to be composed of multiple horizontal lines. The overall effect is abstract and minimalist.

4.5 TREATMENT COMPLIANCE

Compliance will be assured by administration of trial medication in the study centre under supervision of the investigating physician or a designee by the so-called four-eye principle (two-person rule). For this, one authorised employee of the trial site should witness the administration of trial medication, and – if applicable – its preparation (e.g., reconstitution), if correct dosage cannot be ensured otherwise. The measured plasma concentrations and urinary excretion of trial medication will provide additional confirmation of compliance.

Subjects who are non-compliant (for instance, who do not appear for scheduled visits or violate trial restrictions) may be removed from the trial and the CRF will be completed accordingly (for further procedures, please see section 3.4).

5. ASSESSMENTS

5.1 ASSESSMENT OF EFFICACY

Not applicable

5.2 ASSESSMENT OF SAFETY

5.2.1 Physical examination

A complete physical examination will be performed at visit 1 (screening visit/on day -21 to -1) at visit 2 (treatment visit/on day 1 and 2), at visit 3 (follow-up visit 1/on day 5), and at visit 4 (EoT visit/on day 11 to 18). It includes at a minimum appearance, neck, lungs, cardiovascular system, abdomen, extremities, and skin.

The physical examination can be omitted at visit 2 (treatment visit/on day 1) if the subject does not report any health-related changes or abnormalities since the screening visit (see [flow chart](#)).

5.2.2 Vital signs

Vital signs will be evaluated at the time points specified in the [flow chart](#) prior to blood sampling. This includes systolic and diastolic blood pressure and pulse rate (electronically or by palpation count for 1 min) in a seated or supine position after 5 min of rest. All recordings should be made using the same type of blood pressure recording instrument on the same arm if possible. The results must be included in the source documents available at the site.

5.2.3 Safety laboratory parameters

For the assessment of laboratory parameters, blood and urine samples will be collected by the trial site

[REDACTED] The parameters that will be determined are listed in [Table 5.2.3: 1](#) and [Table 5.2.3: 2](#). Reference ranges will be provided in the ISF. Manual differential white blood cell count or urine sediment examinations will only be performed if there is an abnormality in the automatic blood cell count or in the urinalysis, respectively.

Table 5.2.3: 1 Routine laboratory tests

Functional lab group	BI test name [comment/abbreviation]	A ¹	B ¹	C ¹
Haematology	Haematocrit	X	X	X
	Haemoglobin	X	X	X
	Red Blood Cell Count/Erythrocytes	X	X	X
	White Blood Cells/Leucocytes	X	X	X
	Platelet Count/Thrombocytes (quant)	X	X	X
Automatic WBC differential, relative	Neutrophils/Leukocytes	X	-	X
	Eosinophils/Leukocytes	X	-	X
	Basophils/Leukocytes	X	-	X
	Monocytes/Leukocytes	X	-	X
	Lymphocytes/Leukocytes	X	-	X
Automatic WBC differential, absolute	Neutrophil, absolute	X	-	X
	Eosinophils, absolute	X	-	X
	Basophils, absolute	X	-	X
	Monocytes, absolute	X	-	X
	Lymphocytes, absolute	X	-	X
Coagulation	Activated Partial Thromboplastin Time	X	-	X
	Prothrombin time - INR	X	-	X
Enzymes	AST [Aspartate transaminase]/GOT	X	X	X
	ALT [Alanine transaminase]/GPT	X	X	X
	Alkaline Phosphatase	X	X	X
	Gamma-Glutamyl Transferase	X	X	X
	Creatine Kinase [CK]	X	X	X
	Creatine Kinase Isoenzyme MB [if CK is elevated]	-	-	-
Hormones	Thyroid Stimulating Hormone	X	-	-
Substrates	Glucose (Plasma)	X	-	-
	Creatinine	X	X	X
	Glomerular Filtration Rate (GFR)/CKD-EPI ³	X	-	-
	Bilirubin, Total	X	X	X
	Bilirubin, Direct	X	X	X
	Protein, Total	X	-	X
	C-Reactive Protein (Quant)	X	X	X
	Uric Acid	X	-	-
	Albumin	X	-	X
	Globulin	X	-	X
Electrolytes	Albumin/Globulin ratio	X	-	X
	Sodium	X	X	X
	Potassium	X	X	X
	Calcium	X	X	X
	Magnesium	X	X	X
Urinalysis ² (Stix)	Chloride	X	X	X
	Urine Nitrite (qual)	X	-	X
	Urine Protein (qual)	X	-	X
	Urine Glucose (qual)	X	-	X
	Urine Ketone (qual)	X	-	X
	Urobilinogen (qual)	X	-	X
	Urine Bilirubin (qual)	X	-	X
	Urine RBC/Erythrocytes (qual)	X	-	X
	Urine WBC/Leucocytes (qual)	X	-	X
	Urine pH	X	-	X

Table 5.2.3: 1 Routine laboratory tests (cont'd)

Functional lab group	BI test name [comment/abbreviation]	A ¹	B ¹	C ¹
Urine sediment ²	Only positive findings will be reported (for instance, the presence of sediment bacteria, casts in sediment, squamous epithelial cells, erythrocytes, leukocytes)			
Urine creatinine ⁴	Urine creatinine will be determined in urine aliquots obtained from urine collected for PK (in blank sample and in urine from each collection interval)			

- 1) A to be done at screening, B to be done in the morning of day 1, C to be done in the morning of day 2, at the follow-up visit 1 and at the EoT examination
- 2) Microscopic examination if erythrocytes, leukocytes, or protein are abnormal in urine
- 3) Estimated glomerular filtration rate according to CKD-EPI formula [[R12-1392](#)]
- 4) Urine creatinine is not a safety parameter but for technical reasons needs to be listed here as such

The tests listed in [Table 5.2.3: 2](#) are exclusionary laboratory tests that may be repeated as required. The results will not be entered in the CRF/database and will not be reported in the clinical trial report (CTR). Urine pregnancy testing in females will be performed at the screening visit, upon admission to the site in the evening of Day -1 and as part of the EoT examination. Drug screening will be performed at the screening visit and upon admission to the site in the evening of Day -1.

Table 5.2.3: 2 Exclusionary laboratory tests

Functional lab group	Test name
Drug screening (urine)	Amphetamine/MDA Barbiturates Benzodiazepine Cannabis Cocaine Methadone Methamphetamines/MDMA/XTC Opiates Phencyclidine Tricyclic antidepressants
Infectious serology (blood)	Hepatitis B surface antigen (qualitative) Hepatitis B core antibody (qualitative) Hepatitis C antibodies (qualitative) HIV-1 and HIV-2 antibody (qualitative)
Pregnancy test (urine)	Beta human chorionic gonadotropin (beta-HCG)

To encourage compliance with alcoholic restrictions, a breath alcohol test (e.g., Alcotest® 6820 med., Dräger AG, Lübeck, Germany) will be performed during the screening visit, upon admission in the evening of Day -1 and may be repeated at any time during the study at the discretion of an investigator or designee. The results will not be included in the CTR. The laboratory tests listed in [Table 5.2.3: 1](#) and [Table 5.2.3: 2](#) except from the drug screening and pregnancy tests will be performed by the local safety laboratory of the trial site.

Drug screening and pregnancy tests will be performed at the trial site using SureStep ML 10 Scr Test Device; Abbott Rapid Diagnostics, Germany and TestPack+Plus hCG Urine OBC;

Abbott Rapid Diagnostics, Germany, or comparable test systems. Laboratory data will be transmitted electronically from the laboratory to the trial site.

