- 2) International normalized ratio (INR) will be used to calculate Child-Turcotte-Pugh score by sponsor

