## **6.7 BASELINE, TIME WINDOWS AND CALCULATED VISITS**

The last available value determined prior to administration of study cocktail will be defined as baseline.

Adherence to time windows will be checked at the final RPM. Time windows are defined in **Section 6.1 of the CTP**:

*The acceptable deviation from the scheduled time for vital signs, ECG, and laboratory tests will be  $\pm 15$  min.*

Unscheduled measurements of laboratory data and vital signs data will be assumed to be repeat measurements of the most recent scheduled measurement (e.g. for follow-up or confirmation of a particular value). Therefore, unscheduled measurements will be assigned to the planned time point of the previous scheduled measurement.

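### INR, albumin and the white-cell differential are not scheduled on Day 1, so their baselines can be up to 21 days old at dosing while ALT, AST and bilirubin baselines are same-day

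*Protocol*

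**What the plan says.** Protocol 5.2.3, Table 5.2.3: 1, assigns each routine test to panel A, B or C. Its first footnote reads "A to be done at screening, B to be done in the morning of day 1". Panel C covers the morning of Day 2, follow-up visit 1 and the end-of-trial examination. B is therefore the only routine safety panel on the day of dosing, and it is drawn before the cocktail.

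The INR row reads "Prothrombin time - INR X - X": screening yes, Day 1 no, Day 2 onward yes. Albumin and all ten differential rows follow the same pattern, for example "Eosinophils/Leukocytes X - X". ALT, AST and total bilirubin are marked in all three columns.

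Protocol 5.2.1 dates screening as "visit 1 (screening visit/on day -21 to -1". SAP 6.7 states: "The last available value determined prior to administration of study cocktail will be defined as baseline". SAP 7.8.2 applies the same rule to laboratory change from baseline.

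SAP 7.8.1, citing Protocol 5.2.6.1, defines the hepatic-injury AESI for patients with cirrhosis. Baseline INR enters it twice. An abnormal INR is one of the ways into the abnormal-baseline stratum, and within that stratum an INR above 1.2 times baseline is one of the accompanying criteria. The AESI also lists new or worsening eosinophilia above 5%.

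**The concern.** The AESI is meant to pick up liver changes after a single dose. Its parts should share one pre-dose reference point, and here they do not. ALT, AST and bilirubin are compared with the morning of dosing. INR is compared with a value that may be three weeks older. The error can run either way: upward drift before dosing makes the INR limit easier to reach, and downward drift makes it harder.

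The same applies to the descriptive laboratory tables. A Day 2 change from baseline in INR or albumin will be read as the change over one day after the cocktail, but it can include up to three weeks of change before it. The differential matters less. Eosinophilia has a fixed threshold, but judging whether it is new or worse still needs a pre-dose value.

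**Working it through.** The documents give no figure of their own on this point, so the check covers the schedule, the dates and one illustration.

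**1. Which pre-dose values exist**

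| Test | Screening (A) | Day 1 pre-dose (B) | Day 2 onward (C) | Baseline under SAP 6.7 |
|---|---|---|---|---|
| ALT, AST, total bilirubin | yes | yes | yes | Day 1 |
| INR | yes | no | yes | screening |
| Albumin | yes | no | yes | screening |
| White-cell differential | yes | no | yes | screening |

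The Day -1 admission does not fill the gap. Flow-chart footnote 3, read with Protocol 5.2.3, limits those tests to drug screen, breath alcohol, pregnancy and COVID-19. The flow-chart grid is not legible in the text available, so this rests on the table, its footnotes and the flow-chart footnotes.

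**2. Age of the baseline at dosing**

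Admission is on Day -1 and dosing on Day 1, with no Day 0.

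- Earliest screening: Day -21 to Day 1 = 21 days.
- Latest screening: Day -1 to Day 1 = 1 day.
- Longest span behind a Day 2 change from baseline: 21 + 1 = 22 days, of which one day follows dosing.

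An unscheduled pre-dose test would become the baseline and shorten this, but none is planned.

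**3. Effect on the 1.2 x baseline INR limit**

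Let d be the relative INR drift between screening and dosing. The post-dose rise, measured from the true pre-dose value, that just reaches the limit is 1.2/(1 + d) - 1. The values of d are assumptions; the documents give none.

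| Drift d | Calculation | Rise needed |
|---|---|---|
| -10% | 1.2/0.90 - 1 | 33.3% |
| -5% | 1.2/0.95 - 1 | 26.3% |
| 0 (same-day baseline) | 1.2/1.00 - 1 | 20.0% |
| +5% | 1.2/1.05 - 1 | 14.3% |
| +10% | 1.2/1.10 - 1 | 9.1% |

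**4. How far this reaches into the AESI**

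- In the abnormal-baseline stratum the INR criterion counts only together with ALT and/or AST at 2 x baseline or more, or at 300 U/L or more. Those baselines are same-day.
- In the stratum with normal aminotransferases the INR criterion is a multiple of the upper limit of normal, so no INR baseline enters the criterion.
- Albumin is not part of the AESI.
- Healthy volunteers have no AESI, which leaves 12 + 6 = 18 planned patients.

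**5. After the change**

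With these tests in panel B, the maximum age of the baseline falls from 21 days to the morning of dosing.

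**The case against.** The best defence is that the gap is bounded and its consequences are limited. Three weeks is a ceiling, and screening may fall the day before dosing. Patients must have had unchanged treatment for four weeks before the cocktail, which is longer than the gap. The INR criterion never acts alone, alerts are retested within 48 to 72 hours, and the investigator classifies the event. Most of this stands and is why the point is modest. Stable therapy does not guarantee a stable INR or albumin, however, and the plan already repeats bilirubin and the aminotransferases on Day 1.

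Two stronger readings are tempting, and the documents support neither.

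- **Misclassified groups in the primary model.** The Child-Pugh score uses INR and albumin ("International normalized ratio (INR) will be used to calculate Child-Turcotte-Pugh score by sponsor"), class A ends at 6 points and class B starts at 7. A reader might infer that a drift of one point puts a patient in the wrong study group. But Protocol 3.3.2 also separates the groups by history: Group 2 must have had no decompensation event and Group 3 at least one. A drift from 6 to 7 points does not make a Group 2 patient a Group 3 patient, nor does the reverse drift make a Group 3 patient a Group 2 patient. Refitting the model by Day 1 class would create patients who meet neither definition.
- **A false-alert rate.** With an assumed within-patient INR CV of 5% to 10%, 1 - Φ(ln 1.2 / √(2 ln(1 + CV²))) gives 0.5% to 9.8% of patients above 1.2 x baseline by variation alone. That is not an AESI rate. It ignores the required ALT/AST rise, rests on an assumed CV, and has no same-day comparison, although part of this variation would remain with a same-day baseline.

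**Conclusion.** The gap in the schedule is real. INR, albumin and differential baselines can be up to 21 days old at dosing, and the hepatic-injury AESI mixes them with same-day ALT, AST and bilirubin. In the illustration, a 10% drift moves the post-dose INR rise needed from 20% to 9.1% or 33.3%, depending on direction. The effect on AESI counts is likely small, because the INR limit needs an accompanying ALT/AST rise and applies only in the abnormal-baseline stratum. The clearer effect is on the descriptive Day 2 changes in INR and albumin, which cannot be read as one-day changes. The conclusion assumes that no unscheduled pre-dose test is done; the size of any real drift cannot be taken from the documents. Nothing here shows bias in the primary pharmacokinetic comparison. This is an inexpensive improvement to the safety baseline.

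**What to change.** In Table 5.2.3: 1, mark PT-INR for panel B, and with it albumin and the automatic differential, using the existing Day 1 pre-dose venepuncture. SAP 6.7 and 7.8.2 would then take these values as baseline with no change of wording.

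Optionally, list the Child-Pugh score from Day 1 laboratory values beside the screening score, for description only. Because the Day 1 physical examination may be omitted, the listing should state the date of the ascites and encephalopathy items.

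If the Day 1 draws have already been taken, the remaining option lies in the SAP alone: list the screening-to-dosing interval for each subject, and add a footnote to the INR, albumin and differential tables that their baseline comes from screening.

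The cost is one extra coagulation tube and a few routine assays for 30 subjects, plus an edit to the table rows concerned.
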